5.2. Physical Description of Voxelotor

Voxelotor is a synthetic small molecule bearing the chemical name 2-hydroxy-6-((2-(1-isopropyl-1H-pyrazol-5-yl)pyridin-3-yl) methoxy)benzaldehyde. The chemical formula is $C_{19}H_{19}N_3O_3$ and the molecular weight is 337.4 g/mol.

5.3. Dosage Forms

Voxelotor will be supplied as 500 mg tablets, 100 and/or 300 mg dispersible tablets, or 300, 400, 600, and 900 mg powder for oral suspension (packaged as stick packs).

5.4. Packaging and Labeling

Voxelotor tablets and dispersible tablets will be supplied to clinical sites in high-density polyethylene bottles with induction-sealed polypropylene child-resistant caps. The voxelotor powder for oral suspension (packaged as stick packs) will be supplied to clinical sites in a tamper-sealed carton. All study drug packaging must be returned at each visit, regardless of whether they are empty or contain unused study drug.

5.5. Investigational Product Supply

The sponsor or its representative will supply the packaged and labeled drug product to the clinical sites. Study drug will be dispensed at the Day 1 visit and every 3 months thereafter. Participants will receive a 3-month (90-day) supply of study drug at each dispensation visit. Additional details are provided in the Pharmacy Manual.

5.6. Storage and Handling Procedure

Study drug will be stored at controlled room temperature between 15°C and 25°C (59°F to 77°F), in a secure, temperature-controlled, and locked environment with restricted access. The sponsor or its representatives will be permitted, upon request, to audit the study drug supplies, storage, dispensing procedures, and records at any participating site.

5.7. Concomitant and Prohibited Medications

See Section 6.8 for details regarding the definition and recording of concomitant medications.

5.7.1. Prohibited Medications

Use of an investigational product other than that under study in this trial, regardless of its intended use, is prohibited throughout the trial and for 28 days after the last dose.

Voxelotor is a moderate cytochrome P450 (CYP) 3A4 inhibitor and should not be coadministered with sensitive CYP3A4 substrates with a narrow therapeutic index (refer to Table 7 for examples).

Table 7: Sensitive CYP3A4 Substrates with Narrow Therapeutic Index

Sensitive CYP3A4 Substrates with Narrow Therapeutic Index	
Alfentanil, sirolimus, and tacrolimus	

Abbreviations: CYP, cytochrome P450.

Note: **This is not an exhaustive list.** Country-specific lists may be used if available. For an updated list, refer to the following link:

 $https://www.fda.gov/Drugs/DevelopmentApprovalProcess/DevelopmentResources/DrugInteractionsLabeling/ucm093664.htm\#table\ 3-2.$

Concomitant use of voxelotor and moderate or strong inducers of CYP3A4 is not allowed within 30 days of Day 1 or during the study (refer to Table 8 for examples). In the event that concomitant use of voxelotor with a moderate or strong CYP3A4 inducer is unavoidable, the Investigator should contact the Medical Monitor.

Table 8: Examples of Moderate and Strong CYP3A4 Inducers

CYP3A4	Examples
Moderate CYP3A4 inducers	Bosentan, cenobamate, dabrafenib, efavirenz, etravirine, lorlatinib, pexidartinib, phenobarbital, primidone, and sotorasib
Strong CYP3A4 Inducers	Apalutamide, carbamazepine, enzalutamide, ivosidenib, lumacaftor, mitotane, phenytoin, rifampin, and St. John's wort

Abbreviations: CYP, cytochrome P450.

Note: This is not an exhaustive list. Country-specific lists may be used if available.

For an updated list, refer to the following link:

https://www.fda.gov/Drugs/DevelopmentApprovalProcess/DevelopmentResources/DrugInteractionsLabeling/ucm093664.htm#table3-3 (last accessed 30 March 2023).

5.7.2. Other Therapies

Penicillin prophylaxis and vaccinations (including any COVID-19 vaccine) are allowed in accordance with standard of care.

Concomitant medications are allowed, unless the restrictions in Section 5.7.1 apply. Permitted concomitant medications include, but are not limited to, folic acid, commercial medications for the treatment of SCD (eg, HU, L-glutamine, crizanlizumab), over-the-counter- analgesics, and opioids, which are among the chronic medications commonly taken by patients with SCD.

Participants who test positive for acute hepatitis or human immunodeficiency virus (HIV) per standard of care during the study will be discontinued from study drug and will return for the EOS visit.

5.8. Fertility/Contraceptive Requirements

All female participants of childbearing potential (post menarche) should avoid pregnancy, and all sexually active male participants should avoid fathering a child.

5.8.1. Instructions for Female Participants of Childbearing Potential

For female participants of childbearing potential (post menarche) who are sexually active, pregnancy should be avoided by either abstinence from sex/sexual intercourse or the use of highly effective means of contraception for the duration of the study and for a total period of 30 days after the participant has taken her last dose of voxelotor. Highly effective means of contraception are listed in Section 5.9. Pregnancy reporting requirements are outlined in Section 7.4.

Female participants who become pregnant during the study will be withdrawn from the study.

5.8.2. Female Participants of Nonchildbearing Potential

Female participants of nonchildbearing potential are defined as those who have not started their menarche.

5.8.3. Instructions for Male Participants Capable of Fathering a Child

There is no information about the effects that voxelotor could have on the development of the fetus in humans. Therefore, it is important that the partners of male participants do not become pregnant during the study and for a total period of 30 days after the male participant has taken his last dose of voxelotor.

As a precaution, all male participants who are sexually active should avoid fathering a child by either true abstinence or the use of barrier methods of contraception (see Section 5.9).

5.9. Acceptable Forms of Contraception for Sexually Active Participants

For Female Participants:

Highly effective methods of birth control are defined as those that result in a low failure rate (ie, < 1% per year) when used consistently and correctly. Highly effective methods of birth control are as follows:

1. Hormonal contraceptives:

Combined (estrogen- and progestogen-containing) hormonal contraception associated with inhibition of ovulation

- Oral
- Intravaginal
- Transdermal

Progestogen-only hormonal contraception associated with inhibition of ovulation

- Oral
- Injectable
- Implantable

Hormonal contraception must be supplemented with a barrier method (preferably male condom).

Intrauterine device (IUD)

Intrauterine hormone-releasing system (IUS)

Bilateral tubal occlusion

Sexual abstinence:

• Sexual abstinence is considered to be a highly effective method only if the participant is refraining from heterosexual intercourse during the entire period of risk associated with the study treatment. The reliability of sexual abstinence needs to be evaluated in relation to the duration of the clinical study and the preferred and usual lifestyle of the participant.

For Male Participants with Female Partners Capable of Reproduction:

Barrier methods of contraception:

- Condom with occlusive cap (diaphragm or cervical/vault caps) with spermicidal foam/gel/film/cream/suppository for female partner. The use of barrier contraceptives should always be supplemented with the use of a spermicide.
- In addition to a barrier method, the female partner should also use a highly effective contraceptive method as outlined above

5.10. Assessment of Treatment Compliance

Drug disposition records will be maintained, specifying the amount of study drug dispensed to each participant and the date of dispensation. This record will be available for sponsor review at any time. Compliance will be determined by returned tablet/dispersible tablet/stick pack count.

6. STUDY PROCEDURES AND EVALUATIONS

Procedures to be performed during the study are summarized in Section 6.1 through Section 6.13, and scheduled procedures are indicated by visit in the Schedule of Assessments (Appendix A). More frequent assessments, as per Investigator or health-care-provider judgment, will be conducted if needed for management of AEs or per standard of care at each site.

Note: Week 12 and Week 36 planned visits for participants who roll over to this study from Study GBT440-042 will be for drug dispensing, collection of adverse events, and concomitant medications only.

Enrollment in this study, optimally, will occur on the same day as the last visit of the antecedent GBT voxelotor in which participants are eligible to participate in this open-label extension.

Note: The end-of treatment assessments performed upon completion of the antecedent study may serve as the Day 1 assessments for Study GBT440-038 and may be used as the baseline evaluations for Study GBT440-038. The investigational site is not required to repeat the assessments on Day 1 of participation in Study GBT440-038. As these end-of-treatment assessments were performed under the provisions of the antecedent study; it is not considered a protocol deviation if they are used for baseline assessments in Study GBT440-038 prior to obtaining informed consent in Study GBT440-038 since the assessments are covered under the antecedent study.

6.1. Informed Consent/Assent

A signed and dated ICF and/or assent form must be obtained before any protocol-specified eligibility assessments are performed. Care will be taken to avoid coercion of the vulnerable population of parents of children with SCD.

For pediatric participants, consent should be obtained from at least one parent (or both if it is required per clinical site policy) or the participant's legal representative. Guidelines for the informed consent/assent process are outlined in Section 11.2.

6.2. Participant Study Number

Upon execution of informed consent/assent, all participants will be given a unique study number. This number will be used to identify the participant throughout the study and must be used on all study documentation related to that participant.

The interactive response technology (IRT) user manual contains the information needed for registering participant status.

6.3. Inclusion/Exclusion Criteria Review

Eligibility assessment will be conducted prior to receiving study drug on Day 1 of this study. Prior to dosing with study drug, the investigator should determine that the participant is in stable clinical condition.

6.4. Medical History

Ongoing AEs and ongoing concomitant medications from the antecedent studies will be recorded as medical history and concomitant medications, respectively, in this study.

6.5. Height and Weight

Height and weight will be collected for participants < 18 years of age at the time points indicated in the Schedule of Assessments (Appendix A).

6.6. Physical Examination

An abbreviated PE will be completed at the time points indicated in the Schedule of Assessments (Appendix A).

The abbreviated PE will include the following: general appearance; examination of eyes, skin, cardiovascular system, and respiratory system; abdominal examination; and a symptom-directed examination.

6.7. Vital Signs

Vital signs (blood pressure and heart rate) will be measured at the time points indicated in the Schedule of Assessments (Appendix A), after the participant has rested comfortably for at least 5 minutes in the supine or sitting position, as age-appropriate and feasible. If the first vital sign measurement is outside the normal range and deemed clinically significant, the measurement will be repeated within 5 minutes.

6.8. Concomitant Medications

Concomitant medications will be recorded throughout the study at the time points indicated in the Schedule of Assessments (Appendix A).

A concomitant medication is defined as any prescription or over-the-counter preparation, including vitamins and supplements.

In the interest of participant safety and acceptable standards of medical care, the investigator will be permitted to prescribe treatment(s) at his/her discretion. For all study participants, all administered concomitant medications, from signing the ICF/assent form until 28 days (4 weeks) after the participant's last dose of study drug, must be recorded on the participant's eCRF.

All reported concomitant medications will be coded using the current version of the World Health Organization (WHO) Drug Dictionary.

6.9. Adverse Events

AEs and SAEs will be recorded from signing of the ICF/assent form until 28 days after the last dose of study drug. See Section 7 for details regarding the definitions of and reporting requirements for AEs and SAEs.

6.10. Clinical Laboratory Assessments

Blood and urine samples for clinical laboratory tests will be collected at the time points indicated in the Schedule of Assessments (Appendix A).

The clinical laboratory tests that will be performed are listed in Table 9. All tests will be performed at the local clinical laboratory.

Table 9: Clinical Laboratory Tests

He	matology	Serum Chemistry Other
_	Hematocrit	 Alanine aminotransferase Urine pregnancy test ^a
_	Hemoglobin	- Albumin ^b
_	Mean corpuscular hemoglobin	 Alkaline phosphatase
	concentration	 Aspartate aminotransferase
-	Mean corpuscular volume	- Bicarbonate b, c
_	Platelet count	Bilirubin (total, direct, and
_	RBC count	indirect)
_	RBC distribution width	- Blood urea nitrogen
_	Reticulocyte count	- Calcium ^b
	(absolute and percent)	- Chloride ^b
_	WBC count with differential	- Creatinine
	(basophils, eosinophils,	- Glucose ^b
	neutrophils, monocytes,	 Lactate dehydrogenase
	lymphocytes)	- Potassium ^b
		- Sodium ^b

Abbreviations: RBC, red blood cell; WBC, white blood cell.

It is the responsibility of the Investigator or designee to assess the clinical significance of all abnormal clinical laboratory values as defined by the list of normal values on file for the local clinical laboratory. All clinically significant laboratory value abnormalities are to be recorded as AEs.

Additional and repeat clinical laboratory tests for the evaluation of abnormal results and/or AEs during the study may be performed at the discretion of the Investigator or upon request of the sponsor.

6.10.1. Pregnancy Test

Female study participants of childbearing potential will have a urine pregnancy test predose on Day 1 and at defined times during the study as indicated in the Schedule of Assessments (Appendix A). Female study participants with a positive urine pregnancy test on Day 1 will not be eligible to participate in the study.

If a urine pregnancy test is positive, the result must be confirmed per local standard of care (eg, ultrasound, serum pregnancy test).

Female study participants who have not experienced menarche will not undergo pregnancy testing. Should a female participant experience menarche during the study, the participant will be considered to be a female of childbearing potential and will undergo urine pregnancy testing as per the Schedule of Assessments (Appendix A).

6.10.2. Total Blood Volume

On-study blood volume collections will not exceed 2.4 mL/kg in any given 4-week period. Specific blood specimens (eg, exploratory measures) may be omitted at the discretion of the

^a For female participants of childbearing potential.

^b Only record on the CRF if the laboratory value is abnormal and considered clinically significant by the Investigator.

^c After implementation of Amendment 2 record bicarbonate values only; if the local laboratory only provides carbon dioxide values, do not record on the CRF.

Investigator, if warranted, such as in the context of blood loss associated with standard clinical care or bleeding events, or if otherwise deemed appropriate.

Due to total volume restrictions in pediatric research, assessments will be prioritized as indicated in Table 10.

Table 10: Priority of Study Assessments

Priority	Test
1	Hematology
2	Serum chemistry

6.11. Taste and Palatability Questionnaire

Upon introduction of a new dosage form (either powder for oral suspension or dispersible tablets) to participants, a taste and palatability questionnaire will be administered to parents and/or children (aged ≥ 5 years) during the first visit when the transition is made and at the subsequent 2 scheduled visits.

6.12. Sickle Cell Disease–Related Complications

Frequency of SCD-related complications over the course of the treatment period will be recorded for each participant and summarized. SCD-related complications may include, but are not limited to, the following: sickle cell anemia with crisis, acute chest syndrome (ACS), pneumonia, priapism, splenic or hepatic sequestrations, stroke, leg ulcers, and osteonecrosis.

6.13. Transcranial Doppler Ultrasonography

Transcranial Doppler assessments performed as part of standard of care will be recorded on the eCRF. Participants having an abnormal TCD (ie, ≥ 200 cm/sec) during the study will be treated according to the institution's standard of care (eg, initiation of HU or chronic transfusions). Continuation of voxelotor is at the discretion of the investigator.

For participants who discontinued Study GBT440-032 (HOPE Kids 2) as a result of an abnormal TCD \geq 200 cm/sec, TCD assessments will be performed using a Multi-Dop T digital machine manufactured by Compumedics DWL (Germany).

6.14. Missed Assessments

Missed assessments should be rescheduled and performed as close to the original scheduled date as possible. An exception is made when rescheduling becomes, in the investigator's opinion, medically unnecessary or unsafe because it is too close in time to the next scheduled evaluation. In that case, the missed evaluation should be omitted.

7. ADVERSE AND SERIOUS ADVERSE EVENTS

Safety assessments will consist of AE and SAE monitoring, protocol-specified hematology and serum chemistry tests, abbreviated PEs, protocol-specified vital sign measurements, and the results from other protocol-specified tests that are deemed critical to the safety evaluation of voxelotor.

The determination, evaluation, reporting, and follow-up of AEs will be performed as outlined in Section 7.1 and Section 7.2. At each study visit, including phone follow-ups, the study participant or participant caregiver will be asked about any new or ongoing AE since the

previous visit. Assessments of AEs will occur at each study visit. See Section 7.2 for details regarding the required time periods for AE reporting.

Clinically significant changes from study baseline in PE findings, weight, vital signs, and clinical laboratory test results will be recorded as AEs or SAEs, as appropriate.

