Appendix A. SCHEDULE OF ASSESSMENTS

Study Day/Week	Treatment Period								EOS
	First 48 Weeks					After Week 48			+7 days c
	Day 1 a	Week 12 b ± 5 days	Week 24 ± 10 days	Week 36 b ± 10 days	Week 48 ± 10 days	Q12Wk ± 10 days	Q24 Wk ± 10 days	Q48 Wk ± 10 days	
Informed Consent/Assent	X								
Review Inclusion/Exclusion Criteria	X								
Medical History	X								
Weight and Height d	X		X		X			X	
Abbreviated Physical Examination ^e	X				X				
Vital Signs ^f	X	X	X	X	X		X	X	X
Adverse Events	X	X	X	X	X		X	X	X
Concomitant Medications	X	X	X	X	X		X	X	X
Hematology ^g	X	X	X	X	X		X	X	X
Serum Chemistry h	X		X		X			X	X
Urine Pregnancy Test i	X	X	X	X	X		X	X	X
Taste and Palatability Questionnaire with InClinic Dosing ^j	Performed on Day of Switch, and at the following two consecutive visits								
Transcranial Doppler k	Performed as standard of care								
Study Drug Dispensing and Accountability ¹	X	X	X	X	X	X	X	X	X

Abbreviations: CRF, case report form; EOS, End of Study; Q12Wk, every 12 weeks; Q24 Wk, every 24 weeks; Q48 Wk, every 48 weeks; TCD, transcranial Doppler.

Study Day/Week	Treatment Period					EOS			
	First 48 Weeks			After Week 48			+7 days ^c		
	Day 1 ^a	Week 12 b ± 5 days	Week 24 ± 10 days	Week 36 b ± 10 days	Week 48 ± 10 days	Q12Wk ± 10 days	Q24 Wk ± 10 days	Q48 Wk ± 10 days	

Voxelotor

GBT440-038

- a. Day 1 assessments will be performed prior to dosing. If any of the Day 1 assessments were performed at the last study visit in the originating (parent) clinical study, and the Day 1 visit occurs on the same date, the tests do not need to be repeated.
- b. Week 12 and Week 36 planned visits for participants who roll over to this study from Study GBT440-042 will be for drug dispensing, collection of adverse events and concomitant medications only.
- c. The EOS visit should be conducted 4 weeks (28 days) after the last dose of study drug (+7-day window).
- d. Height and weight will be collected only for participants < 18 years of age.
- e. Will include general appearance; examination of eyes, skin, cardiovascular system, and respiratory system; abdominal examination; and a symptom-directed examination.
- f. Heart rate and blood pressure will be measured after participant has rested for ≥ 5 minutes in the seated or supine position. If the first vital sign measurement is outside the normal range and deemed clinically significant, the measurement will be repeated within 5 minutes.

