- g. Will include the following: hematocrit, hemoglobin, mean corpuscular hemoglobin concentration, mean corpuscular volume, platelet count, red blood cell distribution width, reticulocytes (absolute and percent), and white blood cell count with differential.
- h. Will include the following: alanine aminotransferase, albumin, alkaline phosphatase, aspartate aminotransferase, bilirubin (total, direct, and indirect), blood urea nitrogen, creatinine, lactate dehydrogenase. Laboratory values for bicarbonate, calcium, chloride, glucose potassium, and sodium should only be recorded on the CRF if the laboratory value is abnormal and considered clinically significant by the Investigator).
- i. Will be performed for female participants of childbearing potential only. If the urine pregnancy test is positive, the result must be confirmed per local standard of care (eg, ultrasound or serum pregnancy test).
- j. Upon introduction of a new dosage form (either powder for oral suspension or dispersible tablets) or switch to higher dose (ie, modified dispersible tablet) to participants, a brief questionnaire will be administered to parents and/or children (aged ≥ 5 years) during the first visit when the transition is made and at the subsequent 2 scheduled visits.
- k. For all participants, results from TCD assessments performed as part of standard of care at each site will be recorded on the CRF.
- 1 Voxelotor will be dispensed in 12-week (~90-day) intervals with instruction to participants to return any used/unused bottles/stick packs to the clinic. At the Day 1 Visit, only study drug dispensing will be performed. At the EOS visit, only study drug accountability will be performed.

APPENDIX B. SCHEDULE OF ASSESSMENTS FOR SELECT SITES PARTICIPATING IN VOXELOTOR PLASMA AND WHOLE BLOOD PK COLLECTIONS UPON SWITCHING TO THE MODIFIED DOSE DISPERSIBLE TABLETS ^a

Study Day/Week	Day of Switch	14 Days Post-Switch	12 Weeks Post-Switch
PK Sample Collection (plasma and whole blood)	X	X	X
	(Predose)	(Predose)	(Predose)
Other Assessments	Per Scheduled Visit on Day of Switch (Appendix A) and must include Safety Assessments ^b Concomitant Medications Update	Safety Assessments ^b Concomitant Medications Update	Safety Assessments ^b Concomitant Medications Update
Taste and Palatability Questionnaire	X	X	X

Abbreviations: PK, pharmacokinetic.

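### Appendix A omits adverse event collection at the 12-weekly dispensing visit after Week 48, contrary to Section 7; where the grid is followed, the inquiry interval doubles to 24 weeks.

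*Protocol*

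**What the plan says.** Protocol Section 7 sets the inquiry rule, with the look-back running to the visit before: "At each study visit, including phone follow-ups, the study participant or participant caregiver will be asked about any new or ongoing AE since the" (the quotation stops just short of the end of the sentence). It then adds: "Assessments of AEs will occur at each study visit". Neither sentence makes an exception for later years or for dispensing visits.

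Appendix A gives the visit grid. It has nine columns: Day 1, Weeks 12, 24, 36 and 48, then Q12Wk, Q24Wk and Q48Wk after Week 48, and End of Study. The row "Study Drug Dispensing and Accountability" is marked in all nine. The Adverse Events row has eight marks ("Adverse Events X X X X X X X X"), and its empty cell is Q12Wk. The Concomitant Medications row has the same pattern.

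The Q12Wk contact is a scheduled visit with a ±10-day window. The dispensing footnote says: "Voxelotor will be dispensed in 12-week (~90-day) intervals with instruction to participants to return any used/unused bottles/stick packs to the clinic". Section 5.5 likewise describes dispensing every 3 months at a visit.

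Footnote b shortens the Week 12 and Week 36 visits for participants from Study GBT440-042. It says that these visits "will be for drug dispensing, collection of adverse events and concomitant medications only".

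For concomitant medications the timing rule is different: "Concomitant medications will be recorded throughout the study at the time points indicated in the Schedule of Assessments (Appendix A").

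**The concern.** The study exists to describe long-term safety, treatment is open-ended (Protocol Section 3.2), and the conflict begins at Week 48. From then on, a site reading Section 7 asks about adverse events every 12 weeks, while a site reading the grid asks every 24 weeks. Nothing in the protocol says which governs.

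Both endpoints depend on the answer. SAP Section 4 names treatment-emergent and serious adverse events, and the frequency of sickle cell disease-related complications. SAP Section 8.2.3 takes the complications from adverse event records. SAP Section 8.2.2 reports the total number of treatment-emergent events as well as participants affected, so a missed recurrence lowers a planned output even when the participant is already counted.

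The events at risk are those the site learns of only by asking: non-serious events, and complications managed at home or elsewhere. Protocol Section 8 allows summaries by antecedent study, and SAP Section 6.3 allows interim summaries. Groups or data cuts with more follow-up after Week 48 would carry more person-time under the sparser schedule wherever the grid was followed.

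**Working it through.** The documents give no figure on this point, so there is nothing to reproduce. The check reads the grid column by column, computes the inquiry intervals, and adds one illustration that rests on assumptions.

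**1. Is the blank real?** Vital signs, concomitant medications, hematology and the pregnancy test are also empty at Q12Wk and marked at Q24Wk and Q48Wk. The dispensing row has all nine marks. The consistent pattern makes a text-extraction fault unlikely.

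**2. Scheduled inquiries if Appendix A is followed.**
- Adverse event inquiry: Day 1, then Weeks 12, 24, 36, 48, 72, 96, 120, and so on.
- Dispensing: Day 1, then Weeks 12, 24, 36, 48, 60, 72, 84, 96, and so on.
- Visits with dispensing but no scheduled inquiry: Weeks 60, 84, 108, and so on.

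**3. Interval between inquiries.** Inputs are the nominal spacing and the ±10-day windows in Appendix A. The longest interval is the nominal interval + 10 + 10.

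| | Up to Week 48 | After Week 48, grid followed | After Week 48, Section 7 followed |
|---|---|---|---|
| Nominal | 12 × 7 = 84 days | 24 × 7 = 168 days | 84 days |
| Longest with windows | 84 + 20 = 104 days | 168 + 20 = 188 days | 104 days |
| Inquiries per 48 weeks | 4 | 2 | 4 |
| Mean time from event to inquiry, if events are uniform in time | 12 / 2 = 6 weeks | 24 / 2 = 12 weeks | 6 weeks |

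The 104 days before Week 48 is the span from Week 24 to Week 36, or from Week 36 to Week 48. Week 12 has a ±5-day window, so the span from Week 12 to Week 24 is at most 84 + 5 + 10 = 99 days.

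**4. Illustration of what a longer interval could do.** The forgetting rate is an assumption; the documents give none. Let m be the share of events forgotten by 12 weeks, with λ = −ln(1 − m)/12 per week. With inquiry every T weeks, the share captured by recall is (1 − exp(−λT))/(λT).

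For m = 0.20:
- λ × 12 = 0.2231, so capture at 12 weeks is (1 − 0.80)/0.2231 = 0.896.
- λ × 24 = 0.4463, so capture at 24 weeks is (1 − 0.64)/0.4463 = 0.807.
- The ratio is 0.807/0.896 = 0.90.

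In general the ratio reduces to 1 − m/2. If 80% of events reach the record by another route, capture is 0.8 + 0.2 × the recall share. For m = 0.20 that is 0.961/0.979 = 0.98.

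| m (assumed) | Late/early capture, recall only | Late/early capture, 80% captured otherwise |
|---|---|---|
| 0 | 1.00 | 1.00 |
| 0.10 | 0.95 | 0.99 |
| 0.20 | 0.90 | 0.98 |
| 0.30 | 0.85 | 0.97 |

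Any effect would be downward. Its size runs from nil to moderate, depending wholly on two quantities the documents do not supply.

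**The case against.** The strongest reply is that Appendix A need not govern. Section 7 is unconditional. Sections 6.5 to 6.8 and 6.10 send the reader to Appendix A for timing, but Section 6.9 sends the reader to Section 7 for adverse events. A site could reasonably ask every 12 weeks and be compliant. This stands in part: it makes the 24-week interval conditional. It does not settle the matter, because the opening of Section 6 also says that scheduled procedures are shown by visit in Appendix A.

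The blank could also be deliberate, since several other assessments are dropped at Q12Wk. In that case Section 7 should be qualified. Footnote b shows that a dispensing-only visit can include the inquiry; it does not prove what was intended after Week 48.

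Other safeguards limit any loss. Sections 6.9 and 7.2.1 require recording through 28 days after the last dose. Section 7.3 requires serious events to be reported within 24 hours of awareness. Section 5.1.2 provides roughly weekly contact after a dose decrease for an adverse event. These are real, but the first two work only once the site knows of the event, and the third covers only some participants.

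A reader might go further in three ways that the documents do not support:
- **Late event frequencies are biased downward.** This is an inference. No recall or capture rate is given, and the illustration includes no loss at all.
- **A fall in frequency over time is confounded with the change at Week 48.** The SAP plans no early-versus-late comparison of adverse events or complications; its summaries are descriptive and cover the whole study. Tables counting a participant once per preferred term are unaffected by a missed recurrence of a term already recorded.
- **The concomitant medication blank also breaches Section 7.** Section 7 sets no rule for these, and Section 6.8 defers to Appendix A.

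**Conclusion.** The contradiction is established: Section 7 requires adverse event inquiry at every study visit, and Appendix A omits it at a scheduled visit that recurs throughout follow-up after Week 48. At sites that follow Appendix A, the nominal inquiry interval doubles from 12 to 24 weeks, and the longest interval with windows rises from 104 to 188 days. At sites that follow Section 7, nothing changes. Practice may therefore differ between sites.

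The consequence is a possibility, not a demonstrated bias. Non-serious events and sickle cell complications managed without site contact may be under-ascertained in long-term follow-up, and the planned total count of treatment-emergent events could be lowered as a result. Serious events are less exposed. The size cannot be set from the documents: the 0.85 to 1.00 range on recall alone, and 0.97 to 1.00 with 80% capture by other routes, both rest on assumed forgetting of 0% to 30% by 12 weeks.

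The point is worth correcting because it touches ascertainment of both endpoints and costs almost nothing to repair.

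**What to change.** Reconcile the two passages by marking Adverse Events in the Q12Wk column of Appendix A, so that the inquiry Section 7 already requires is made at the existing dispensing visit. This returns the scheduled interval to a nominal 12 weeks (at most 104 days) and makes practice uniform across sites. Concomitant Medications may be marked in the same column for consistency; that is optional, since there is no conflict to resolve.

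If the lighter schedule was intended, Section 7 must instead be qualified and the change in ascertainment after Week 48 disclosed when results are reported. That removes the contradiction but leaves the longer interval.

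The cost of the preferred change is one cell in the schedule, or two with concomitant medications, and a few minutes of site time per visit. No extra visit or procedure is needed.
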